- g 24-hour Holter monitor, to be performed at screening, and at any time the physician believes it is medically appropriate.
- h A full physical exam will occur every 3 cycles. Symptom-directed assessments will be conducted per standard clinical practice.
- i Should occur every 3 cycles.
- j A serum pregnancy test will be performed for women of childbearing potential during screening and predose on Cycle 1, Day 1. The serum pregnancy test may be collected up to 3 days before dosing. The results must be available and negative before the first dose of MLN9708 is administered.
- k Hematology and chemistry panels may be collected up to 3 days prior to dosing. Criteria for retreatment are provided in Section 6.5.2. After 24 cycles on treatment, hematology and chemistry laboratory evaluations may be done to monitor the patient according to standard clinical practice per the treating physician.
- l Repeat as clinically indicated by change in serum creatinine. Creatinine clearance will be calculated based on a 24-hour urine collection at screening. eGFR will be calculated according to the equations in Section 15.1. 24-hour urine for protein is required to assess amyloid renal involvement/ response.
- m If abnormal, a diagnostic work up should be performed and the patient treated and stabilized before administering MLN9708. PT/INR and PTT may be repeated during the treatment period at the discretion of the investigator if bleeding occurs or as clinically indicated.
- n Only for patients in the extension cohort after every cycle.
- o Repeat every treatment cycle, at the EOT visit, and every 6 weeks during the PFS follow-up period.
- p CCI
- q Bone marrow biopsy and aspirate should be repeated at the discretion of the investigator as clinically indicated and if response is documented by other parameters, and at EOT. Immunohistochemistry of dominant clonal plasma cells is recommended.
- r To be performed at screening and at any time the physician believes there are symptoms or signs that suggest increased or new bone lesions. Plain films of symptomatic sites for signs or symptoms of new bone lesions may be obtained instead of a full skeletal survey. A PET-CT may be done at screening in

Study Procedures	Screening ^a	Treatment Period					End of Treatment ^d	Follow-up	
		CYCLES 1 -12 ^b						PFS ^e (± 1 wk)	OS ^f (± 1 wk)
	Days	Days				Every 6 weeks		Every 6 weeks	Every 12 weeks
	-28 to -1	1 ^c	8	15	Rest Period 22 to 28	Every 6 weeks		Every 12 weeks	Every 12 weeks

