6. AL Amyloidosis Risk stage I or II disease.

Staging system defined by: NT-proBNP cut off of < 332 pg/mL and troponin T cut-off of 0.035 ng/mL as thresholds. Stage I, both under threshold; Stage II, either troponin or NT-proBNP [but not both] over threshold; if troponin T not available at local institution, troponin I may be used, but threshold is < 0.1 ng/mL. ⁽⁵⁷⁾

7. Must be relapsed or refractory after at least 1 prior therapy for AL amyloidosis and, in the investigator's opinion, requires further treatment.

NOTE: If a patient has received a transplant as his/her first therapy, he/she must be at least 3 months posttransplantation and recovered from the side effects of the stem cell transplant.

Any patient who was not a candidate for high-dose therapy and was unable to tolerate an alkylating agent plus a corticosteroid (eg, melphalan plus prednisone) or patients who are intolerant to an alternative prior therapy after receiving at least 1 cycle of such therapy because of severe adverse events

(eg, hypersensitivity reaction) also can be considered for enrollment after discussion with the Millennium clinician.

8. Patients must have an Eastern Cooperative Oncology Group (ECOG) status of 0 to 2 (see Section 15.3)
9. Clinical laboratory values as specified below within 3 days before the first dose of study drug (unless otherwise noted):
 - a. echocardiographic ejection fraction $\geq 40\%$ within 28 days before the first dose of study drug.
 - b. platelet count $\geq 75 \times 10^9/\text{L}$.
 - c. neutrophil count $\geq 1.0 \times 10^9/\text{L}$.
 - d. total bilirubin $\leq 1.5 \times \text{ULN}$.
 - e. alkaline phosphatase $\leq 5 \times \text{ULN}$.
 - f. alanine aminotransferase (ALT) and aspartate aminotransferase (AST) $\leq 3 \times \text{ULN}$.
 - g. eGFR $\geq 45 \text{ mL/min}/1.73 \text{ m}^2$ (see Section 15.1 for the Equation to Estimate Glomerular Filtration Rates).
10. Female patients who:
 - Are postmenopausal for at least 1 year before the screening visit, OR
 - Are surgically sterile, OR
 - If they are of childbearing potential, agree to practice 2 effective methods of contraception, at the same time, from the time of signing the informed consent through 30 days after the last dose of study drug, or agree to completely abstain from heterosexual intercourse.
11. Male patients, even if surgically sterilized (ie, status postvasectomy), who:

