5.2 Exclusion Criteria

1. Known allergy to any of the study medications, their analogues, or excipients in the various formulations.
2. Treatment with any investigational products within 28 days before the first dose of study drug.
3. Requirement for other concomitant chemotherapy, immunotherapy, radiotherapy, or any ancillary therapy considered to be investigational.
4. Failure to have fully recovered (ie, \leq Grade 1 toxicity) from the effects of prior chemotherapy regardless of the interval since last treatment.
5. Cardiac system:
 - a. QTc $>$ 470 milliseconds (msec) on a 12 lead ECG obtained during the Screening period. If a machine reading is above this value, the ECG should be reviewed by a qualified reader and confirmed on a subsequent ECG.
 - b. AL Amyloidosis Risk Stage III disease. Staging defined by: NT-proBNP cut off of $<$ 332 pg/mL and troponin T cut-off of 0.035 ng/mL as thresholds: stage III, both over threshold; if troponin T not available at local institution, troponin I may be used, but threshold is $<$ 0.1 ng/mL⁽⁵⁷⁾
 - c. New York Heart Association (NYHA) classification III or IV. See Section 15.4 for criteria.
 - d. Enzyme-documented myocardial infarction within 6 months before enrollment.
 - e. Chronic atrial fibrillation.
 - f. Grade 2 or 3 atrioventricular (AV) block (Mobitz, Type I permitted).
 - g. Sustained ($>$ 30 seconds) ventricular tachycardia, more than 1 episode of nonsustained ventricular tachycardia (defined as 3 consecutive ventricular beats), or frequent ($>$ 20/24 hours) ventricular pairs, detected by 24-hour ambulatory electrocardiographic monitoring.
 - h. Supine systolic blood pressure $<$ 90 mmHg, or symptomatic orthostatic hypotension, or a decrease in systolic blood pressure on standing of $>$ 20 mm Hg in spite of being treated for orthostatic hypotension.
 - i. History of a bleeding diathesis or currently receiving treatment with warfarin. Patients are allowed to take aspirin.

7. GI system:

- a. Severe diarrhea (\geq Grade 3) not controllable with medication (such as octreotide) or requires administration of total parenteral nutrition.
- b. Known GI disease or GI procedure that could interfere with the oral absorption or tolerance of study drug, including difficulty swallowing.

8. Neurologic/ Social system:

- a. Patients with \geq Grade 2 peripheral neuropathy or painful peripheral neuropathy on clinical examination will be excluded.

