- b. Previous or ongoing psychiatric illness and/or social situations that would limit compliance with study requirements.

9. Systemic infections:

- a. Known to be human immunodeficiency virus (HIV)-positive.
- b. Known to be hepatitis B surface antigen-positive or has known or suspected active hepatitis C infection.
- c. Uncontrolled infection requiring systemic antibiotics.

10. Other malignant disease/s:

- a. Clinically overt multiple myeloma (bone marrow plasma cells \geq 30%), and at least 1 of the following: bone lesions, anemia (< 100 g/L), and hypercalcemia.
- b. Patients with amyloidosis due to mutations of the transthyretin gene (see Section 15.2).
- c. Patients with non-AL amyloidosis (see Section 15.2).
- d. Presence of other active malignancy with the exception of nonmelanoma skin cancer, cervical cancer, treated early-stage prostate cancer provided that prostate-specific antigen is within normal limit, or any completely resected carcinoma in situ.

11. Female patients who are lactating or pregnant.

12. Major surgery within 14 days before the first dose of study drug.

13. Systemic treatment with strong inhibitors of CYP1A2 (fluvoxamine, enoxacin, ciprofloxacin), strong inhibitors of CYP3A (clarithromycin, telithromycin, itraconazole, voriconazole, ketoconazole, nefazodone, posaconazole) or strong CYP3A inducers

(rifampin, rifapentine, rifabutin, carbamazepine, phenytoin, phenobarbital), or use of Ginkgo biloba or St. John's wort within 14 days before the first dose of study treatment.

14. Any other serious medical or psychiatric illness that could, in the investigator's opinion, potentially interfere with the completion of treatment according to this protocol.

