6.7 Excluded Concomitant Medications and Procedures

The following medications and procedures are prohibited during the study.

Systemic treatment with any of the following metabolizing enzyme inhibitors is not permitted during this study. The rationale for this is that in the event of a drug-drug interaction with an inhibitor, MLN9708 exposure would be increased leading to a high probability of an AE.

- Strong inhibitors of CYP1A2: fluvoxamine, enoxacin, ciprofloxacin
- Strong inhibitors of CYP3A: clarithromycin, telithromycin, itraconazole, voriconazole, ketoconazole, nefazodone, and posaconazole

Systemic treatment with any of the following metabolizing enzyme inducers should be avoided, unless there is no appropriate alternative medication for the patient's use. The rationale for this (unlike with inhibitors) is that in the event of a drug-drug interaction with an inducer, MLN9708 exposure would be decreased, leading to a reduced chance of toxicity and potentially a reduced chance of efficacy.

- Strong CYP3A inducers: rifampin, rifapentine, rifabutin, carbamazepine, phenytoin, and phenobarbital
- ACE inhibitors (ACE inhibitors should be used with caution and requires consultation with the Millennium clinician. Patients with AL amyloidosis usually poorly tolerate ACE inhibitors, not due to possible interaction with MLN9708, but because of symptomatic hypotension due to an underlying involvement of the autonomic nervous system. Therefore, ACE inhibitors should be excluded in patients with eGFR < 60mg/min/1.72 and in those whom orthostatic systolic blood pressure is < 100 mmHg.)
- Excluded foods and dietary supplements include St. John's wort and Ginkgo biloba
- Warfarin (aspirin is allowed)

The following procedures are prohibited during the study:

- Any antineoplastic treatment with activity against AL amyloidosis, other than study drugs

- Radiation therapy (note that, in general, the requirement for local radiation therapy indicates disease progression)
- Platelet transfusions to help patients meet eligibility criteria are not allowed within 3 days prior to study drug dosing

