6.8 Permitted Concomitant Medications and Procedures

All necessary supportive care consistent with optimal patient care shall be available to patients as necessary.

The following are examples of those permitted during the study:

Growth factors (eg, granulocyte colony stimulating factor [G-CSF], granulocyte macrophage-colony stimulating factor [GM-CSF], recombinant erythropoietin) will not be allowed in Cycle 1, but may be considered in Cycle 2 and beyond although caution must be exercised.

Patients should be transfused with red cells and platelets as clinically indicated.

Antiviral therapy such as acyclovir may be considered.

Concomitant treatment with bisphosphonates will be permitted.

Patients who experience worsening neuropathy from baseline may be observed for recovery, and any supportive therapy or intervention may be initiated as appropriate at the discretion of the investigator. Dose reduction is suggested, when and if the patient resumes MLN9708 therapy.

Standard amyloid supportive guidelines that should be considered include:

Patients who experience fluid retention or congestive heart failure (CHF) may be treated with intravenous diuretics.

Patients who experience life-threatening ventricular arrhythmias or atrial arrhythmias with hemodynamic instability should be treated according to standard clinical practice guidelines

Compression garments and midodrine for patients with symptomatic orthostasis

Note: Such adverse events may still qualify as a DLT depending on the severity and timing of their occurrence (see Section 6.3.1).

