7.5.10 Clinical Laboratory Evaluations

Handling of clinical laboratory samples will be outlined in the Study Manual. Decisions regarding eligibility for this study may be made using local laboratory determinations. For dosing decisions, local hematology and chemistry laboratory results may be used.

Hematology and chemistry panels may be collected up to 72 hours prior to dosing. Criteria for retreatment are provided in Section 6.6.

Clinical Chemistry and Hematology

Blood samples for analysis of the following clinical chemistry and hematological parameters will be obtained as specified in the [Schedule of Events](#). After 24 cycles on treatment, hematology and chemistry laboratory evaluations may be done to monitor the patient according to standard clinical practice per the treating physician.

Hematology

- Hemoglobin
- Hematocrit
- Platelet count
- WBC count with differential

Serum Chemistry

- Blood urea nitrogen (BUN)
- Creatinine
- Total bilirubin
- Uric acid
- Lactate dehydrogenase
- Alkaline phosphatase
- AST
- ALT
- Albumin
- Glucose
- Sodium
- Potassium
- Chloride
- CO₂
- Magnesium
- Calcium
- Phosphate

Urinalysis

- Appearance and color
- pH
- Specific gravity
- Protein
- Ketones
- Bilirubin
- Blood
- Nitrite
- Urobilinogen
- Glucose
- Leukocytes
- Microscopic assessment

24-Hour Urine Collection

- Total protein
- Creatinine

Coagulation Studies

- Prothrombin time and international normalized ratio
- Activated partial thromboplastin time

Hormones

- Thyrotropin (TSH)
- Cortisol

Other

- Cardiac Markers:
BNP, NT-ProBNP, and troponin T or I
- β 2-microglobulin

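### The 3-day ban on platelet transfusions given to meet eligibility is counted back from dosing, not from the qualifying count, so its protection of that count shrinks from 3 days to 0 as the sample gets older

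*Protocol*

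**What the plan says.** Protocol Section 6.7, among its prohibited procedures, states: "Platelet transfusions to help patients meet eligibility criteria are not allowed within 3 days prior to study drug dosing". The 3 days are counted back from dosing, and the ban is limited by purpose to transfusions meant to secure eligibility.

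The platelet limit is inclusion criterion 9b in Section 5.1, at least 75 x 10^9/L. The heading of criterion 9 sets its timing: "Clinical laboratory values as specified below within 3 days before the first dose of study drug". Footnote k of the Schedule of Events gives the same lead ("Hematology and chemistry panels may be collected up to 3 days prior to dosing"), and Section 7.5.10 gives it in hours ("Hematology and chemistry panels may be collected up to 72 hours prior to dosing"). Footnote c lets Day 1 evaluations be done before dosing on the day or up to 3 days earlier, so the Day 1 hematology entry does not force a fresh count.

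Section 6.8 permits other platelet support without a time limit: "Patients should be transfused with red cells and platelets as clinically indicated".

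No section of the protocol or SAP sets a transfusion-free interval before the sample or requires the qualifying count to be unsupported.

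**The concern.** Section 6.7 is written to stop a transfusion from carrying a patient over the eligibility limit. Eligibility is decided by the count, so the interval that matters for that aim is from transfusion to sample. The rule fixes a different interval, from transfusion to dose. When the sample is drawn early, the two come apart, and a transfusion just outside the ban can shortly precede the deciding count.

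What is at stake is the integrity of one entry criterion, and with it some patient safety. Section 1.3 lists thrombocytopenia among the most common treatment-related reactions to this drug. Three DLT criteria in Section 6.3.1 rest on platelets, and Section 6.5.2.1 uses the same 75 x 10^9/L limit for starting the next cycle. A patient whose unsupported count is below the limit could enter without any written rule being broken.

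**Working it through.** The plan states no interval between transfusion and count, so there is no figure of its own to reproduce. The interval follows from two inputs:

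- Length and anchor of the ban: 3 days before dosing (Section 6.7).
- Age of the qualifying sample at dosing, s: 0 to 3 days (criterion 9; footnotes c and k; Section 7.5.10, 72 hours).

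**Days counted as 24-hour periods (an assumption).** For a transfusion the ban covers, the latest permitted time is 3 days before dosing. The guaranteed interval before the count is therefore 3 − s days. If the ban ran back 3 days from the sample and continued to the first dose, the interval would be 3 days for every s, and the ban would reach back 3 + s days before dosing.

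| Sample age s (days) | Guaranteed interval now | Interval if tied to sample | Reach of ban before dosing if tied to sample |
|---|---|---|---|
| 0 | 3 − 0 = 3 days (72 h) | 3 days | 3 + 0 = 3 days |
| 1 | 3 − 1 = 2 days (48 h) | 3 days | 3 + 1 = 4 days |
| 2 | 3 − 2 = 1 day (24 h) | 3 days | 3 + 2 = 5 days |
| 3 | 3 − 3 = 0 days (0 h) | 3 days | 3 + 3 = 6 days |

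The interval is under 24 h only for samples drawn more than 48 h before dosing, which is the earliest 24 h of the 72 h window. At the edge, a transfusion 73 h before dosing and a count 72 h before dosing are 1 h apart, and both are allowed.

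**Days counted as calendar days.** The ban covers the three calendar days before dosing, so the latest permitted transfusion is on the fourth day before. A sample on the third day before then follows it with no full calendar day between. The number of full transfusion-free calendar days before the sample day is again 3, 2, 1 and 0 for s = 0, 1, 2 and 3. The one-hour edge case does not carry over literally, but the gap can be as short as overnight.

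**Clinically indicated transfusions.** The ban does not apply to them, so the guaranteed interval is 0 for every s, including a Day 1 sample.

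**Whether other text closes the gap.**

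- Exclusion 4 concerns failure to recover "from the effects of prior chemotherapy regardless of the interval since last treatment"; a low count from another cause is outside it.
- The bleeding exclusion ("History of a bleeding diathesis or currently receiving treatment with warfarin") does not address a supported count.
- Exclusion 14 turns on the investigator's view that another serious illness could "potentially interfere with the completion of treatment according to this protocol".
- The Schedule has a separate Screening hematology entry, which may show an earlier low value, but criterion 9 tests only the value within 3 days of the first dose.
- Section 6.1 requires criteria to be met and documented before dosing; a supported count meets them.

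These safeguards narrow the gap but do not close it.

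**The case against.** The strongest reply is that nothing here is contradictory: a pre-dose ban and a 3-day laboratory window can both be followed as written, and no harm can be derived from the documents. They give no transfusion frequency and no figure for how long a transfusion raises the count. The problem needs an unsupported count below the limit, a transfusion for eligibility just outside the ban, and an early sample. Covered patients still have 3 transfusion-free days before dosing. The platelet-count DLT thresholds (below 25,000/mm³ for at least 7 days, or below 10,000/mm³) lie well under the entry limit. All of this stands. It sets the weight of the point but does not put the anchor in the right place.

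Two further objections limit the claim. The step from 3 days down to 0 describes only transfusions given for eligibility, because Section 6.8 allows clinically indicated ones at any time. The hour-level figures depend on reading days as 24-hour periods; only the laboratory sentence in Section 7.5.10 uses hours.

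A reader might infer that every platelet transfusion before the sample should be barred. The stated purpose of Section 6.7 does not support that. Section 6.8 expressly permits clinically indicated support, and Section 1.1.1 stresses the need for a rapid response in this disease. A blanket rule goes beyond the defect and is a separate choice for the sponsor.

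**Conclusion.** The point holds as a minor drafting weakness. For transfusions given to meet eligibility, the protection of the qualifying count is 3 days minus the age of the sample, falling to 0 at the earliest permitted sample on the 24-hour reading and remaining short on the calendar-day reading. For clinically indicated transfusions there is no guaranteed interval now.

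A reader might go further and infer that DLT rates, the 3 + 3 decisions or an endpoint are distorted. The documents do not support that: they give neither how often this would happen nor how large or lasting the effect on the count would be, and the situation is probably uncommon. Nor do they support a claim that such a transfusion would go unrecorded. The Schedule of Events collects concomitant treatment from the first dose, whereas Section 8.1.8 refers to collection from screening.

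The 3-day length is the sponsor's own figure. The documents do not show that it is long enough for the effect of a transfusion to clear, so the conclusion concerns where the interval is anchored, not how long it should be. Whether the ban also applies to the platelet limit for later cycles is not stated, and nothing here depends on it.

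**What to change.** In Section 6.7 and criterion 9b, state that platelet transfusions to help patients meet eligibility criteria are not allowed within 3 days before the qualifying platelet sample, or between that sample and the first dose. Leave the 3-day laboratory window unchanged.

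The cost is one sentence in two places and an occasional re-sample. For a transfusion already covered by the ban, dosing cannot take place until 3 days after it. Sample and dose could both fall at that point, so the change adds no wait beyond laboratory turnaround.

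Optionally, the sponsor may apply the same 3-day sample rule to clinically indicated transfusions. They would stay permitted, but an occasional patient would need a re-sample or would wait up to 3 days plus turnaround.

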6.8 Permitted Concomitant Medications and Procedures

All necessary supportive care consistent with optimal patient care shall be available to patients as necessary.

The following are examples of those permitted during the study:

Growth factors (eg, granulocyte colony stimulating factor [G-CSF], granulocyte macrophage-colony stimulating factor [GM-CSF], recombinant erythropoietin) will not be allowed in Cycle 1, but may be considered in Cycle 2 and beyond although caution must be exercised.

Patients should be transfused with red cells and platelets as clinically indicated.

Antiviral therapy such as acyclovir may be considered.

Concomitant treatment with bisphosphonates will be permitted.

Patients who experience worsening neuropathy from baseline may be observed for recovery, and any supportive therapy or intervention may be initiated as appropriate at the discretion of the investigator. Dose reduction is suggested, when and if the patient resumes MLN9708 therapy.

Standard amyloid supportive guidelines that should be considered include:

Patients who experience fluid retention or congestive heart failure (CHF) may be treated with intravenous diuretics.

Patients who experience life-threatening ventricular arrhythmias or atrial arrhythmias with hemodynamic instability should be treated according to standard clinical practice guidelines

Compression garments and midodrine for patients with symptomatic orthostasis

Note: Such adverse events may still qualify as a DLT depending on the severity and timing of their occurrence (see Section 6.3.1).

